Following informed consent and once a participant has been screened and meets inclusion criteria a baseline assessment will be performed. Participants will then be randomly assigned to either the holistic yoga program (HYP) or the wellness lifestyle program (WLP). The randomization process will be directed by [name]. (statistician) using a program within the REDCap database. Randomization will be stratified by gender (men vs. women) and veteran/non-veteran status. Within strata, randomization with block sizes of 4 will be executed to ensure balance. Once an eligible participant has signed informed consent, been screened, and has completed the baseline measures the project coordinator will obtain the randomization from the REDCap database. The participant identifier and date are recorded. To ensure allocation concealment, only the project coordinator, [name] and [name] will have access to the randomization function within REDCap (and will not conduct outcome assessments). The research assistant who will conduct outcome assessments will be blinded to group assignment. No one will be allowed access to randomization assignment until all baseline measures have been completed.

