5.0 Study Procedures

- Following informed consent and once a participant has been screened and meets inclusion criteria per the screening interview, a baseline assessment will be performed. The baseline assessment includes collection of sociodemographic data, substance use, psychiatric treatment utilization history, and assessments of PTSD (CAPS) and PTSD symptoms (self-reported PTSD symptoms, anger, sleep, anxiety, depression), and related outcomes (pain, well-being, quality of life, interoceptive awareness, and self-regulation). Substance use will be measured with 2 items. Alcohol use disorders will be assessed with the Alcohol Use Disorders Identification Test Consumption (AUDIT-C), which is commonly used in primary care settings, including VA primary care⁶⁶ and corresponds reasonably well with the full AUDIT⁹⁰. It can be scored continuously from 0 to 12, with higher scores representing riskier drinking, or categorically, with cutpoints of 3 for women and 4 for men having good sensitivity and specificity for hazardous drinking. Other substance use will be measured with the 10-item Drug Abuse Screening Test (DAST)⁹¹ which has shown to have good test-retest reliability, validity, and sensitivity, and specificity in detecting problem substance use⁶⁹.

See **Table 1** below for the administration schedule for all measures and time estimates for the assessment batteries.

Table 1. Outcome Assessment Protocol: Measures and Schedule of Administration

Domain	Measure	Items	Time (min)	Schedule				
				Screen	BL	8 wk FU	4 Mo FU	7 Mo FU
Demographics and Covariates	Screening Interview – Eligibility	22	10	X				
	Demographic/Covariate Form (BL/FU) AUDIT-C alcohol use DAST – drug use	21/12)	(7/3)		X	X	X	X
Overall PTSD Symptoms	CAPS – Clinician Interview	30	45	X			X	X
	PCL – Self Report	20	6		X	X	X	X
PTSD-Specific Symptoms	PROMIS Anger Short Form	5	2		X	X	X	X
	MOS – Sleep	12	3		X	X	X	X
PTSD-Related Outcomes	BDI – Depression	21	7		X	X	X	X
	STAI – Anxiety (state only)	20	5		X	X	X	X
	BPI – Pain	11	3		X	X	X	X
	SF-20 – Well-being/quality of life	20	6		X	X	X	X
Other Related Outcomes	MAIA - Interoceptive Awareness and /Self Regulation	32	10		X	X	X	X
	SCS-SF-Self compassion	12	3		X	X	X	X
	NGSES – self-efficacy	8	3		X	X	X	X
	Mental Illness Stigma	6	2		X	X	X	X
	FACIT-SP - spirituality	12	3		X	X	X	X
Treatment Factors	PPQ – Treatment Credibility	5	2		X			
	CSQ-8 – Client Satisfaction	9	3				X	
	Program Evaluation Questionnaire	10	8				X	

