
Treatment Factors will be assessed by three measures. The Pre-Program Questionnaire (PPQ)⁸¹ is an adaptation of Borkovec and Nau’s format⁸² and is a frequently used measure of treatment credibility. The questionnaire asks subjects to rate how confident they are in the program, how logical the program seems,

how successful they think it will be, how helpful the program leaders will be, and whether they would recommend the program to a friend, on a 10-point Likert-type scale. Treatment Satisfaction will be measured by the Client Satisfaction Questionnaire (CSQ-8), an 8-item scale that uses a 4-point likert scale to indicate participants' appraisal of their satisfaction with the intervention.⁸³ The CSQ-8 has excellent internal consistency, with a coefficient alpha of .87-.93, and evidence for the construct and concurrent validity of this measure has been reported as well.⁸⁴ A one-hour Program Evaluation Focus Group will be conducted with 15 randomly selected HYP participants to gather detailed information about participants' experience of the intervention to guide improvement of its structure and content. These participants will receive \$15 for completing the interview. [name], a sociologist experienced in qualitative methods, will train a member of the study staff to conduct the interviews, which will be audio recorded and transcribed. [name] will explore the data in order to understand participants' perceptions of the program, particularly in relation to PTSD, using Grounded Theory, an emergent constant comparative method.⁸⁹ The secondary analysis (Situational Analysis), will map all major features of participants' characteristics, perceptions, material elements and settings, in order to understand the relations and differences among them. All other participants will complete a brief program evaluation questionnaire with open-ended questions to ascertain likes and dislikes as well as suggestions for improvement of HYP or WLP. Treatment Engagement will be assessed by examining totals of treatment sessions attended and home practice completed.

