Study questionnaires, rating scales, and other assessments will be completed by study participants through an on-line survey or paper questionnaires (when the participant is unable to use the on-line survey and to capture home practice), assisted if needed by trained study staff blinded to condition. When on-line surveys are used to capture data, participants will be provided with a survey link and a code which will allow them to access the survey. The survey link will be sent to the participant in an email from Outlook on the VA network. The access code will be provided to the participant separately by another method, such as a hard-copy presented in-person, verbally over the phone, or a STREEM text. Data will be entered from paper self-report questionnaires or interviews conducted by trained study staff (e.g. CAPS). Within the REDCap database, algorithms will be created to check for inappropriate or missed data entry. Computer algorithms will automatically score questionnaires within the same database. These data will be backed up daily onto a password protected, secured server at the IU School of Medicine. Participant social security numbers, names, addresses and other personally identifiable information will be restricted to authorized personnel to protect confidentiality and will be stored in a separate password protected Microsoft Access Database on the RVAMC secured server. We have experience in setting up data integrity protocols and data back-up to minimize the risk for lost or inaccurate data. Participant personally identifiable information will be restricted to authorized personnel to protect confidentiality. We have experience using this strategy successfully in previous research, accurately completing assessments, protecting patient privacy and minimizing the risk for lost or inaccurate data. For our current PTSD study, audits revealed very low rates of data entry error (0.00079 or 0.079%) and missing data (average of 0.00083 or 0.083%). We have used similar length or longer batteries of measures in several previous or current trials without over-burdening patients. Self-report assessments will be completed via on-line surveys (REDCap) and interviews will be conducted in-person as we have found that rapport is more easily established face-to-face. If multiple attempts have failed for on-line surveys and/or in-person interviews, we have employed two strategies to capture outcome assessments: (1) conduct assessments by phone; and (2) mail questionnaires with postage paid, self-addressed envelope to our office. At times in past studies, participants have needed assistance to cover the cost of driving to the RVAMC for an assessment, especially if they live more than 30 minutes away. In these situations, the Project Coordinator may authorize a \$10 gas card to defray the round trip cost of travelling to a scheduled study visit for assessment purposes. We have previously arranged taxi cab rides to and from our VA. To maintain participant confidentiality, our study staff will adhere to careful interview and data collection procedures. First, participants will be told that their responses will remain confidential and that every effort will be made to fulfill that assurance. Second, the interviews will be conducted in an appropriate setting (i.e., private interview room). Third, any completed paper surveys will be stored in a secure location in our locked RVAMC office in a locked file cabinet. The screening and assessment interviews and study databases (using Microsoft Access) will be designed by trained study staff under the direction of [name] or the Project Manager.

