
Once baseline assessments are completed, the participant will be randomly assigned to the Holistic Yoga Program (HYP) or Wellness Lifestyle Program (WLP). The Holistic Yoga Program (HYP) arm will involve a standardized 16-week, yoga intervention consisting of: 1) a program orientation session conducted by a yoga instructor; 2) once weekly in-person group yoga class (postures, breathing practices, deep muscle contraction practices, relaxation practices) taught by a yoga instructor registered with Yoga Alliance at a minimum of the 200 hour level; 3) audio recordings of guided yoga postures, breathing, and relaxation practices for home-use; 3) a handbook to reinforce concepts taught during in-person session. Patients randomized to the Wellness Lifestyle Program (WLP) arm will participate in a standardized 16-week intervention that will consist of: 1) a program orientation conducted by a trained member of the study staff; 2) once weekly in-person group wellness classes (didactics and discussion of wellness topics and low intensity physical activity consisting of walking taught by a clinical psychologist with experience in trauma with consultation available from an experienced athletic trainer; 3) a handbook to reinforce wellness concepts and physical activity instructions taught during in-person session and to assist with home practice. After completing the program, participants will be asked to complete the same assessments as baseline with the addition of 2 program evaluation questionnaires. To minimize the potential for ascertainment bias, follow-up assessments (8 weeks, 4 months, 7 months) will be conducted by on-line survey and the interviews by a trained research assistant who will be blinded to treatment assignment. Participants will receive \$25 for completing the 8-week assessments, \$35 for completing the 16-week assessments and \$45 for completing the 7-month follow-up assessment. Those who fail screening will be given \$15.

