We will conduct both interventions on a continuous schedule so that interested participants may begin the intervention immediately without having to wait for an entire cohort to be recruited. The Holistic Yoga Program (HYP) and Wellness Lifestyle Program (WLP), will both provide one 90-minute session each week for 16 weeks. The first session for each participant will consist of an orientation session with a trained member of the study staff. Group sessions will average 7-8 participants with the upper limit of 15 participants.. We may offer an additional 16-week session in years 2-4 if needed to recruit adequate numbers of participants to accommodate participants who are unable to attend the ongoing class day/time. Sessions will be held in a large multipurpose room at the RVAMC or the National Guard Armory at Stout Field or a classroom at the Regenstrief Institute on [name] (a block from RVAMC). Attendance will be recorded to assess adherence. If a participant is assigned to an intervention class that meets at a location offsite and paid parking is required, study staff will provide a parking voucher to the participant at the end of each class attended in order to cover the cost of parking.

6.0 Reporting of Adverse Events or Unanticipated Problems involving Risk to Participants or Others

Adverse events that are expected and do not pose additional risk to participants will be reported at the time of continuing review. Adverse events that pose risk to participants and unanticipated problems will be reported to the IRB within 5 business days of becoming aware of the event. The event will be reported using the "Prompt Reporting Form for VA Research" and will be submitted both to the IU IRB and the Indy VA Research Compliance and logged by the Project Coordinator.

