8.0 Statistical Considerations

RELIEVE will involve a 2-arm, parallel group, RCT. Since participants cannot be blinded to treatment assignment, observed outcomes (if positive) could be affected by expectation bias. To account for this potential bias, we will assess treatment expectations at baseline and account for them in our analyses. We will

randomize at the patient level rather than the provider level for two reasons (1) randomization at patient level saves sample size; and (2) patients from the same provider in the two arms will be adjusted for “provider effect.” Contamination will also be low because there is relatively minimal involvement required of VA providers in RELIEVE. In addition, randomization will be stratified by veteran and non-veteran status and gender (4 strata) to avoid potential imbalance of these factors between the two arms. [name], PhD (statistician) will create a randomization scheme in REDCap for each of the four strata to randomize patients in blocks of 4 assignments within each of 4 stratum.

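### As scheduled, treatment expectation is measured before allocation, so adjusting for it cannot account for bias that arises because participants know their arm

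*Combined protocol and SAP*

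**What the plan says.** Section 8.0 notes that participants cannot be blinded and that positive results could therefore reflect expectation. Its remedy is: "To account for this potential bias, we will assess treatment expectations at baseline and account for them in our analyses".

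On timing, section 4.0 says: "No one will be allowed access to randomization assignment until all baseline measures have been completed". Section 5.0 gives the same order, with assignment following the baseline assessments. The schedule of measures in section 5.0 (Table 1, Outcome Assessment Protocol) lists "PPQ – Treatment Credibility" with 5 items, 2 minutes and one mark, in the baseline column. No other scheduled instrument measures expectation or credibility.

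On content, the Treatment Factors paragraph of section 5.0 says the PPQ asks, among other things, "how successful they think it will be, how helpful the program leaders will be, and whether they would recommend the program to a friend". It refers to a single program and gives no time of completion.

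On use, section 8.0 names the baseline credibility score twice: under the main analysis, as an example of covariates that will be considered, and under the secondary-outcome paragraph, as one of several exploratory moderators tested by interaction with arm.

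**The concern.** The bias that section 8.0 describes begins when a participant learns which program he or she will attend. Someone who hoped for yoga and is assigned to the wellness program may expect less, and someone assigned to yoga may expect more. A score collected before that moment cannot record the change.

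A report that followed section 8.0 literally would say that expectation bias had been accounted for when it had not. As scheduled, the trial would also hold no data on expectation for the assigned program, and such data cannot be recovered later. The exposure is greatest for the PCL, which section 5.0 lists with CAPS as a primary measure and which is the only primary measure taken at 8 weeks, and for the self-reported secondary outcomes.

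**Working it through.** **Plan's own figures.** Sample size (section 8.0): difference 15.4, SD 28, so d = 15.4/28 = 0.55. By the normal approximation with 85% power and two-sided 5%, n = 2 × (1.960 + 1.036)² / 0.55² = 59.4, so 60 per arm. Then 60 × 1.35 = 81, and (81 × 2)/0.70 = 231.4, so 232. The plan's numbers reproduce; 81 evaluable per arm is used below.

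**Is the baseline-only mark a table artefact?** The row times in the schedule, with the PPQ's 2 minutes counted at baseline only, sum to 62, 56, 112 and 101 minutes at baseline, 8 weeks, 4 months and 7 months. The stated totals are 67, 61, 117 and 106. Each is 5 minutes higher, and the offset is constant only if the PPQ counts at baseline and nowhere else. This supports its being given once. It does not show whether it precedes assignment; that comes from the ordering statements in sections 4.0 and 5.0.

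**What adjustment does.** Let A be arm, Z the pre-allocation score and E expectation once the arm is known. Suppose E differs by arm by a gap g, and the outcome changes by b per unit of E. With no true effect, the apparent arm effect is b × g. Randomization makes Z independent of A, so including Z leaves the expected coefficient of A at b × g.

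An illustration with assumed inputs not in the documents: 6 CAPS points per SD of expectation, gap 0.5 SD, correlation of Z with E of 0.3 or 0.6, no true effect, 81 per arm, 4,000 simulated trials each. The spurious benefit is 6 × 0.5 = 3.0 points by construction.

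| Analysis | r = 0.3 | r = 0.6 |
|---|---|---|
| Unadjusted | 2.93 | 3.08 |
| Adjusted for Z | 2.93 | 3.09 |
| Adjusted, with arm × Z | 2.94 | 3.09 |

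The Monte Carlo standard error is about 0.07. The simulation illustrates the argument and is not separate evidence, because Z is independent of arm by construction.

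**What the moderation test does.** With standardised credibility and no other covariates, the interaction has SE = sqrt(2/81) = 0.157. The effect detectable with 80% power is (1.96 + 0.84) × 0.157 = 0.44 SD of outcome per SD of credibility. The planned model adjusts for the baseline outcome. The documents give no baseline-outcome correlation; if it is assumed to be 0.5 to 0.7, the figure is 0.44 × sqrt(1 − 0.25) = 0.38 to 0.44 × sqrt(1 − 0.49) = 0.31.

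A gap that is the same at every level of credibility produces no interaction at all. If the gap rises with prior credibility (assumed: 0.5 + 0.5z, slope 0.3), the interaction is 0.3 × 0.5 = 0.15, and the power to see it without covariates is 15.9%. The bias at mean credibility is still 0.3 × 0.5 = 0.15.

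**What a post-allocation score could do.** With 116 per arm, SE = sqrt(2/116) = 0.131, so the arm difference in expectation would have a 95% half-width of 1.96 × 0.131 = 0.26 SD and 80% power for 2.80 × 0.131 = 0.37 SD. Adjusting the outcome for such a score is not safe as a primary analysis. In a simulation with gap 0.5 SD and slope 0.3 it moved a bias of 0.149 SD to −0.001, but to −0.042 when an unmeasured cause loaded 0.3 on both expectation and outcome.

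**The case against.** **The baseline score has real uses.** This stands. It can correct chance imbalance, add precision and show whether the effect varies with prior credibility. Where the gap depends on prior credibility, the interaction model also carries information: in the rising-gap example the bias one SD below the mean is 0.3 × (0.5 − 0.5) = 0. What neither use removes is the average bias.

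**The PPQ may have been meant for after allocation.** This stands as a possibility. Its name, its reference to one program and its leaders, and the absence of credibility from the narrative list of baseline content in section 5.0 all fit that reading. Expectation for the assigned program would then be measured. But no section schedules it so, and using it as an ordinary covariate would then adjust the intention-to-treat effect for something that allocation can change. The text needs correcting on either reading.

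**The powered outcome is protected.** Largely so. The sample size rests on CAPS at 4 months, which has a blinded interviewer, and both arms receive one 90-minute session a week for 16 weeks. Blinding the interviewer does not blind the participant who reports the symptoms, but the concern is smaller there.

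**Stronger readings that the documents do not support.** A reader might infer that the CAPS result will be biased in favor of yoga by some stated amount. Nothing in the documents gives the size or direction of any expectation gap. A reader might also apply the 1.35 design effect to the moderation test. Section 8.0 derives that factor for the comparison of arms, where a whole class shares an arm; credibility varies within class. In simulation with classes of 8 and ICC 0.05, the SE of the arm effect rose to 0.186 while that of the interaction stayed at 0.159.

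**Conclusion.** The statement in section 8.0 claims a property that the design, as scheduled, lacks. If the PPQ precedes allocation, adjusting for it removes none of the average bias from an expectation gap that arises once the arm is known; this follows from randomization and needs no assumed effect size. The planned interaction is only a weak check, with 80% power for about 0.44 SD per SD of credibility without covariates (0.38 to 0.31 under the assumed correlations).

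The size and direction of the bias itself are unknown. Purely as an assumed range, a gap of 0.25 to 0.75 SD and a slope of 0.2 to 0.4 would give 0.25 × 0.2 = 0.05 to 0.75 × 0.4 = 0.30 SD on a self-reported outcome.

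The conclusion rests on the schedule and ordering as written, and on reading the expectations in section 8.0 as the PPQ, which is inferred because no other scheduled instrument fits. It should be corrected, but it does not undermine the primary model or the sample size.

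**What to change.** 1. **Restate section 8.0.** Describe the baseline score as adjusting for prior expectation only, not for bias from knowing the arm. Say in the main-analysis paragraph whether it is in the model.
2. **Settle the timing.** Reconcile sections 4.0 and 5.0 (the assignment rule, the schedule, the PPQ description and the procedures) on when the PPQ is given and which program it rates.
3. **Keep the pre-allocation PPQ and repeat it once.** The covariate and moderator analyses need the baseline score, so the PPQ should not simply be moved. Give it again for the assigned program, after allocation and before the first class, at the same point relative to orientation in both arms. Section 5.0 needs reconciling here too: it gives the yoga arm "a program orientation session conducted by a yoga instructor", but later says: "The first session for each participant will consist of an orientation session with a trained member of the study staff".
4. **Limit its use.** Compare the repeated score between arms. Use it otherwise only in a labelled sensitivity or mediation analysis that states its assumption of no unmeasured confounding, never in the primary intention-to-treat model.

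**Cost.** Items 1 and 2 are text only. Item 3 takes about 2 minutes per participant, at most 232 × 2 = 464 minutes over the trial, with no extra visit; item 4 adds one analysis. Blinding needs care: section 5.0 has questionnaires "assisted if needed by trained study staff blinded to condition", and an arm-specific PPQ could reveal the arm. Collect it online or through staff who do not assess outcomes. The added analysis can inform the question but not settle it, because its assumption cannot be tested. The primary model and sample size do not change.

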Sample size. Our sample size is calculated based on estimated differences of intervention effects between two arms on the primary outcome: CAPS total score at 4 months, or treatment end. The CAPS total score is a continuous measure (0-136) and reflects a combined score reflecting symptom frequency and symptom severity. A recently published yoga pilot study for patients with PTSD⁹ found a pre-treatment CAPS score of 77.33 (standard deviation = 28.6). Post-treatment scores were reduced by 34% (CAPS = 51.1, SD = 27.6, effect size = 0.9) from the yoga intervention. We powered on a medium effect size of 0.55 which requires a larger sample size than 0.9. We recognize the correlation of outcomes from subjects within the same yoga class may reduce the effective sample size compared to the same sample with independent observations. This possible “clustering effect” has implications for power. Randomization will occur at the individual not cluster or clinic level. Also, we expect that the intra-cluster correlation (ICC) will be near zero because groups will have a mixture of participants from the various recruitment sites: therefore, there is no reason to believe that participants within groups would be more correlated on the outcomes than participants from different groups. We have no preliminary data to estimate the intra-cluster correlation (ICC) for participants within the same group. However, based on similarly designed published studies, we expect the ICC to be relatively small and balanced across the two treatment arms since the cluster sizes will be similar. We will assume an ICC of 0.05 for both groups. We will also assume a 20% difference between treatment groups. The absolute score difference at 4 months is estimated to be approximately 15.4 points (61.6, 80% of 77). Assuming a common standard deviation of 28 and using a two-sample t-test, we will need 60 evaluable subjects in each arm to detect such a difference (Cohen’s $d = 0.55$) with >85% power and 5% Type I error rate. With approximately 8 subjects per treatment group/class session or cluster, the design effect is $1 + (8-1) \times 0.05 = 1.35$. Therefore, we will inflate our sample size by 35% to accommodate the potential clustering effects. We then need 81 evaluable subjects in each arm. With an assumed 30% attrition, we will then need $(81 \times 2) / 0.70 = 232$ subjects (116 in each arm).

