Data analysis: Baseline characteristics of the RELIEVE sample. To evaluate representativeness, we will compare enrollees and those who decline enrollment on baseline characteristics (socio-demographic variables, psychiatric comorbidity, and current and prior PTSD treatments). Any differences will be considered when interpreting results of subsequent analyses. We will also examine differences in baseline characteristics between patients who remain in the study and those who dropout. The linear mixed modeling approach (see next section) will ensure that all available data are used for subjects who have missing data. The models will also incorporate dropout status to adjust for follow-up missing data pattern. All participants will have baseline data. The possible missing data patterns will be (1) missing 4 month, not 7 month, (2) missing 7 month, not 4 month, (3) missing both 4 and 7 months, and (4) complete data.

Main analysis of the primary outcome. Our main analysis will use the ANCOVA (analysis of covariance) approach to linear mixed modeling of repeated measures in which the baseline measure of the relevant outcome scores (i.e., CAPS or PCL) is adjusted as a covariate in the model.⁸⁵ The model for CAPS will be adjusted for baseline CAPS score. The model for PCL, a continuous measure with a possible range of 17-85, will be adjusted for baseline PCL score. The CAPS and PCL are measured at every time point (baseline, 8 weeks, 4 months, 7 months) except the CAPS is not administered at 6 weeks in order to reduce participant burden, since the CAPS and PCL are highly correlated. We plan an intent-to-treat analysis with the primary endpoint at 4 months and evaluation of “early” response at 8 weeks and “sustained” response at 7 months (3 months post-intervention). The models will simultaneously incorporate three post-baseline measures (8 weeks ([PCL only], 4 months, and 7 months) of the relevant response variable. The main predictors will be group (treatment arm), time (categorical with indicator variables to avoid restrictive assumption of linearity over time), and their interaction. A random intercept will be used to adjust for the potential clustering effect for patients in

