Missing data.⁸⁷ Based on our prior studies, we anticipate a possible dropout rate of 30%, which is reflected in the sample size calculation. We will first run a logistic model with missing status as the response variable, intervention arm, patients’ demographic characteristics as covariates, to check whether the missing status depends on the intervention group assignment and patient characteristics. Second, our linear mixed effects model can accommodate missing-at-random (or MAR which is assumed in many trials) where no bias will be introduced by ignoring the missing-data mechanism. If drop-outs are Missing Not At Random (MNAR), meaning the likelihood of drop-out depends on an un-observed outcome, and the missing data mechanism is ignored, potential bias can be introduced. We will run sensitivity analyses using linear mixed models with the “multiple imputation” method and 100 generated data sets to compare results with the standard linear mixed effects modeling without imputation to assess the robustness of the inference.

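### Participants with neither a 4-month nor a 7-month CAPS add nothing to the primary CAPS analysis and their PCL scores go unused, so the 4-month contrast can be biased if symptom-driven dropout differs by arm

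*Combined protocol and SAP*

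**What the plan says.** Section 8.0, Sample size, names the "primary outcome: CAPS total score at 4 months, or treatment end" as the basis for the calculation. The assessment schedule in Section 5.0 places CAPS at screening, 4 months and 7 months, and PCL at baseline, 8 weeks, 4 months and 7 months. Section 8.0, Main analysis of the primary outcome, agrees that the 8-week row is for PCL alone. (One sentence there says 6 weeks where the schedule has 8.) It justifies omitting CAPS at that visit by the strong correlation between the two scales.

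For the model itself: "The model for CAPS will be adjusted for baseline CAPS score". Each model takes as outcomes only the post-baseline values of its own scale.

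On missing data, Section 8.0 makes five statements:

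- The mixed model "will ensure that all available data are used for subjects who have missing data".
- Dropout status will be put into the models, in a form not described.
- Four missing-data patterns are possible, defined by the 4- and 7-month visits; the third is "3) missing both 4 and 7 months".
- A logistic model of missingness will use "intervention arm, patients’ demographic characteristics as covariates, to check whether the missing status depends on the intervention group assignment" and patient characteristics.
- The mixed model is valid if data are missing at random (MAR), and a sensitivity analysis will use multiple imputation with 100 data sets. The variables in the imputation model are not stated.

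**The concern.** A mixed model uses every available outcome value, but only values of the outcome being modelled. With baseline CAPS on the right-hand side, a participant in the third pattern has no CAPS outcome and does not affect the arm comparison, even with a PCL on file from week 8. A later PCL may also exist without a CAPS, because Section 5.0 collects questionnaires online or by mail while CAPS needs an interview.

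This matters because of what MAR means here. In the CAPS model it conditions on arm, baseline CAPS and any covariates added. Early response to a 16-week program is a plausible reason for being lost, and the 8-week PCL is the trial's measure of it, yet it is not in the model. If loss depends on it differently in the two arms, the 4-month contrast is shifted and the MAR assurance in Section 8.0 does not cover the shift. The logistic check lists no symptom score, so it cannot reveal the dependence.

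**Working it through.** **The plan's own figures.** Inputs from Section 8.0, Sample size: "The absolute score difference at 4 months is estimated to be approximately 15.4 points"; "Assuming a common standard deviation of 28 and using a two-sample t-test"; "with >85% power and 5% Type I error rate". I take the test as two-sided, which is not stated.

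- Standardised difference: 15.4 / 28 = 0.55.
- n per arm = 2 × (1.960 + 1.036)² / 0.55² = 59.4, rounded up to 60. Power at 60 per arm is 85.4% by the normal formula and 84.8% by the noncentral t.
- Design effect: 1 + 7 × 0.05 = 1.35, and 60 × 1.35 = 81 per arm.
- Attrition: 162 / 0.70 = 231.4, hence 232.

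The stated sample size reproduces, and this point does not change it.

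**Who can be lost.** 0.30 × 232 = 69.6, so up to about 70 people (about 35 per arm). This is an upper limit: those who miss 4 months but return at 7 stay in the model.

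**Whether the existing provisions recover them.**

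- Dropout-status term: the third pattern has no post-baseline CAPS from which to estimate a dropout effect.
- Logistic check: it describes missingness by arm and demographics and does not alter the estimate.
- Multiple imputation: if built from the mixed model's own variables, it returns essentially the same answer. If it includes the PCL, it can help. The plan does not say which.

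**How large the bias could be.** The documents give no correlations and no dropout mechanism, so the following are assumptions. Baseline CAPS, 8-week PCL and 4-month CAPS were simulated (2 million subjects per scenario, SD 28, true HYP advantage 15.4, half of it present at week 8). About 30% were lost before 4 months, with loss depending only on the 8-week PCL. The 7-month visit and class clustering were left out. The table shows the HYP advantage estimated by ANCOVA on observed CAPS. Columns give the correlations baseline/8-week, 8-week/4-month and baseline/4-month; OR is the odds ratio of loss per SD of 8-week PCL.

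| Loss depends on 8-week PCL | 0.5, 0.6, 0.4 | 0.6, 0.7, 0.5 | 0.6, 0.8, 0.5 |
|---|---|---|---|
| Alike in both arms, OR 1.65 | 15.28 | 15.30 | 15.20 |
| Alike in both arms, OR 2.72 | 14.90 | 14.87 | 14.88 |
| HYP only, OR 1.65 | 16.99 | 16.99 | 17.42 |
| HYP only, OR 2.72 | 18.24 | 18.33 | 19.03 |

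Subtracting 15.4, the bias is 0.1 to 0.5 points toward the null in the first two rows and 1.6 to 3.6 points in favour of HYP in the last two. Other assumed correlations (8-week/4-month 0.60 to 0.75, baseline/4-month 0.5) widen the one-arm range to about 1.3 to 3.8. With dependence in both arms but mildly unequal (OR 2.7 against 2.0, or 2.0 against 1.65), the bias is about 0.4 to 0.9. With OR 1.3 in HYP only it is about 0.7 to 1.0. Placing the strong dependence in WLP instead reverses the sign.

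With no true effect and OR 2.72 in HYP only, the model shows a spurious advantage of about 2.9 points. In a separate simulation of 1,000 trials with 116 per arm it rejected in 10.7% to 18.3% of trials instead of 5%.

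Imputing 4-month CAPS by arm from baseline CAPS and 8-week PCL gave 15.3 to 15.5 in every true-effect scenario tabulated. Recovery is expected by construction, since loss was made to depend on that PCL alone. If only half of those lost have an 8-week PCL, roughly half of the bias is removed.

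**The case against.** The strongest reply is that the plan already does much to limit the problem, and most of it stands.

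A reader might infer that everyone who leaves before 4 months is excluded. The documents do not support that. The analysis is intent-to-treat, and Section 5.0 provides phone assessments, mailed questionnaires and travel help. Someone who stops attending but is assessed remains in the model, as does someone who misses 4 months and returns at 7.

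A reader might also call the all-available-data sentence simply false. It describes the approach for both scales, and the PCL model does use the 8-week value. For CAPS, every observed post-baseline CAPS is used. The sentence is too broad rather than wholly wrong. Likewise, the four patterns are complete for CAPS, which has no 8-week visit.

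A third inference is that the sensitivity analysis would miss the bias. The plan does not say the imputation leaves out the PCL; it is silent. The fair criticism is that the imputation model is unspecified.

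Finally, the larger biases need moderate or strong dependence in one arm and none in the other, and the documents offer no evidence of that. What remains is that the main CAPS analysis has no route by which the PCL can inform the comparison, and neither the dropout term nor the logistic check supplies one.

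**Conclusion.** The point holds in a limited form. Participants with no 4- or 7-month CAPS contribute nothing to the 4-month contrast, their PCL data are unused in it, and the all-available-data statement is not true for CAPS. That much follows from the text.

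That the primary result is biased is a further step that the documents do not support; it can be. The size rests wholly on assumed correlations, 30% loss and an assumed dropout mechanism: about 0 to 0.5 points of 15.4 if dependence on early symptoms is equal in both arms, 0.4 to 0.9 if mildly unequal, and 1.3 to 3.8 (8% to 25% of the target: 1.3/15.4 and 3.8/15.4) if moderate to strong in one arm only. It may favour either arm. This is a worthwhile correction to the analysis plan, not a flaw in the design or the sample size.

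**What to change.** In Section 8.0, Missing data, specify the imputation that is already planned. Impute 4- and 7-month CAPS separately by arm, from baseline CAPS and PCL, 8-week PCL, and 4- and 7-month PCL where present, with class membership handled consistently with the class random intercept in the analysis model. A joint CAPS-PCL repeated-measures model would serve equally. Report the resulting 4-month contrast for all randomised participants beside the main model; it need not replace it.

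Add baseline CAPS and 8-week PCL to the logistic missingness model. In the Data analysis paragraph, limit the all-available-data statement to what each model actually uses.

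The cost is analysis work: a somewhat more complex imputation model, with no new data and no change to 232. The limit is that it helps only for participants who gave a post-baseline PCL before being lost. Fixing the variables in advance also removes a choice that would otherwise be made after the data are seen.
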